14.1 Table 1: Baseline characteristics before and after adjustment

Variable	9,		After adjustment			
			Referent	Exposure	Std. diff.	
Number of patients			-			-
Age categories						
•••						

14.2 Table 2: Follow-up time

Patient Group	Median Follow-Up Time (Days) [IQR]
Overall Patient Population	
Referent	
Exposure	

14.3 Table 3: Censoring events

	Overall	Referent	Exposure
Outcome			
Death			
Start of an additional exposure			
End of index exposure			
Specified date reached			
End of patient data			
End of patient enrollment			

14.4 Table 4: Results from primary analysis

Analysis	No. exposed events	No. referent events	Exposed rate	Referent rate	HR (95% CI)
Crude					
Analysis 1					

HR, Hazard Ratio; CI, Confidence Interval.

	Exposure: Zoledronic acid (5 mg) 15-minute intravenous administration every year for 3 years vs. placebo Reference: Placebo Aim: To evaluate the effect of annual infusions of zoledronic acid on fracture risk during a 3-year period in postmenopausal women with osteoporosis All patients received oral daily calcium (1000 to 1500 mg) and vitamin D (400 to 1200 IU).	Exposure: new-use of Zoledronic acid (washout 450 days) NDC Generic Name: ZOLEDRONIC ACID ZOLEDRONIC ACID IN MANNITOL & WATER FOR INJECTION ZOLEDRONIC ACID IN MANNITOL AND 0.9 % SODIUM CHLORIDE ZOLEDRONIC ACID IN MANNITOL AND WATER FOR INJECTION ZOLEDRONIC ACID IN MANNITOL AND WATER FOR INJECTION NDC codes: 143964201, 16729024231, 17478032705, 25021080167, 42023015101, 43598033011, 47335003540, 47333096241, 54288010001, 5511106850755150026605, 67457039054, 68001036625, 78035084, 78038725, 409421501, 409421505, 16714081501, 17478032745, 23155017031, 25021080166, 45963044055, 51991006598, 53150087101, 60505611000, 63232096198, 68001036622, 78043561, 78059061, 409422801, 43598033111, 51991006498, 55111068852, 63323096600, 67457061910, 67457079410, 70860021051 CPT/HCPCS Procedure Codes: C9115, 13487, 13488, 13489, Q2051, Q4095 Reference of primary analysis: Raloxifene (proxy of placebo) Reference of primary analysis: Raloxifene (proxy of placebo)		Criteria	
	PRIMARY	DUTCOME		Adequate mapping in claims	
	Hip fracture (Dual-energy x-ray absorptiometry of the hip was performed at baseline and at months 6, 12, 24, and 36 for bone loss) - both patients in stratum 1 and stratum 2	Measured 1 day after drug initiation (codes reported in "Hip and femur fractures codes": Hip and femur fractures Algorithm include the following case-qualifying (CO): CQ = 1 Inpatient claim with primary diagnosis code AND CQ = 2 Inpatient claim with secondary diagnosis code AND CQ = 3 Non-inpatient claim with diagnosis code AND HCPCS in (27125, 27130, 27220, 27222, 27226-27228, 27230-27248, 27254, 27254, 27267-27269, 27500-27514) OR Non-inpatient claim with diagnosis code AND ICD-9 Procedure Code in (7855, 7905, 7915, 7925, 7935, 7965, 8151, 8152)	Wright NC, Daigle SG, Melton ME, Delzell ES, Balasubramanian A, Curtis JR. The Design and Validation of a New Algorithm to Identify Incident Fractures in Administrative Claims Data J. Bone Miner Res. 2019 Oct;34(10):1798-1807. doi: 10.1002/jbmr.3807. Epub 2019 Aug 5. PMID: 31170317.	Intermediate mapping in claims	
	New Vertebral Fractures [only in patients who were not taking any osteoporosis medications at the time of randomization] only patients in stratum 1 (Spinal lateral radiographs were obtained at baseline and at 12, 24, and 36 months or early termination for patients in stratum 1 and at baseline and at 36 months or early termination for patients in stratum 2)	Measured 1 day after drug initiation: Vertebral Fractures: Algorithm include the following case-qualifying (CO): CQ = 1 Inpatient claim with primary diagnosis code AND CQ = 2 Non-inpatient claim with diagnosis code AND HCPCS in (22305, 22310, 22315, 22318, 22319, 22325-22328, 22510-22515, 22520-22525, 27200, 27202, 72291, 72292, 76012, 76013, 77082, 77085, 77086, 52360-52363) AND CQ = 3 Non-inpatient claim with diagnosis code AND HCPCS in (99024, 99058, 99201-99215, 99241-99245, 99271-99285, 99301-99355, 99366, 99385-99387,99395-99404, 99429, 99499) [Physician E&M codes] plus, up to 10 days earlier (or on the same day), Outpatient claim with HCPCS in (72010-72159, 72240-72285, 72295) [Spine imaging codes]	Outcome not included in the final analysis Wright NC, Daigle SG, Melton ME, Delzell ES, Balasubramanian A, Curtis JR. The Design and Validation of a New Algorithm to Identify Incident Fractures in Administrative Claims Data. J Bone Miner Res. 2019 Oct;34(10):1798-1807. doi: 10.1002/jbmr.3807. Epub 2019 Aug 5. PMID: 31170317.	Poor mapping or cannot be measured in claims	
	INCLUSION	CRITERIA		Can't be measured in claims but not important for the analysis	
1	Postmenopausal women between the ages of 65 and 89 years	Female, 65-89 years at the time of drug initiation			
2	Bone mineral density T score of -2.5 or less at the femoral neck, with or without evidence of existing vertebral fracture, or a T score of -1.5 or less, with radiologic evidence of at least two mild vertebral fractures or one moderate vertebral fracture.	Measured time of enrollment to prior to the day of drug initiation inpatient (any position), outpatient (any position): Osteoporosis diagnosis ICD-9 diagnosis: 733.00, 733.01, 733.02, 733.03, 733.09, 733.13 ICD-10 diagnosis: M81.0, M81.6, M81.8, M80.88*, M80.08* OR Measured time of enrollment to 730 days (2 years) prior to the day of drug initiation: Alendronate, Ibandronate, Risedronate, Pamidronate, Etidronate, Tiludronate		Adequate mapping in claims of criteria extracted from clinicaltrial.gov (ESLD and Svere eye disease), after clinical review with FDA (Abaloparatide, Romosozumab) or from the protocol of Horizon-recurrent (all other criteria in blue): "Colôn-Emeric CS, Caminis J, Suh TT, Pieper CF, Janning C, Magaziner J, Adachi J, Rosario-Jansen T, Mesenbrink P, Horowitz ZD, Lyles KW; HORIZON Recurrent Fracture Trial. The PHORIZON Recurrent Fracture Trial: the prevention of subsequent fractures after low trauma hip fracture repair. Curr Med Res Opin. 2004 Jun;20(6):903-10. doi: 10.1185/03079904125003683. PMID: 15200749." Protocol of Horizon-pivotal not available - numerous unsuccessful attempts had been made to retrive it from the authors	

	EXCLUSION	CRITERIA	
1	Bisphosphonate users such as Aredia® (pamidronate), Didronel® (etidronate), Fosamax® (alendronate), Actonel® (risedronate), Skelid® (tiludronate)	Measured 730 days (2 years) prior to the day of drug initiation: Generic names: Alendronate, Ibandronate, Risedronate, Pamidronate, Etidronate, Tiludronate	
2.1	Previous use of: (1) any previous use of parathyroid hormone	Measured 730 days (2 years) prior to the day of drug initiation: Generic names: Brand names: Natpara® (parathyroid hormone), Forteo®, Bonsity (teriparatide), Tymlos® (abaloparatide)	
2.2	(2) use of anabolic steroids or growth hormone within 6 months before trial entry	Measured 180 days prior to the day of drug initiation: AASs: Generic names: TESTOSTERONE, DIHYDROTESTOSTERONE PROPIONATE, ESTROGENS, ESTERIFED/METHYLTESTOSTERONE, TESTOSTERONE CYPIONATE, MICRONIZED, TESTOSTERONE CYPIONATE ESTERADIOL CYPIONATE, TESTOSTERONE ENANTHATE-ESTRADIOL OVALERATE, TESTOSTERONE MICRONIZED, TESTOSTERONE UNDEC ANOATE, METHYLTESTOSTERONE, MICRONIZED, STANOLONE, OXYMETHOLONE, NANDROLONE PIENPROPIONATE, OXANDROLONE, STANOZOLO, FLUDXYMESTERONE, TESTOSTERONE ENANTHATE, TESTOSTERONE PROPIONATE, NANDROLONE DECANOATE, METHYLTESTOSTERONE, TESTOSTERONE CYPIONATE GHS: Generic names: SOMATROPIN, TESAMORELIN ACETATE Brand names: OMNITROPE, SAIZEN, ZOMACTON, GEREF, HUMATROPE, NUTROPIN, SEROSTIM, ZORBTIVE, EGRIFTA, MACRILEN, NORDITROPIN FLEXPRO, GENOTROPIN, TEVEROPIN	
2.3	OR (3) oral or intravenous systemic corticosteroids within 12 months,	Measured 30 days prior to the day of drug initiation: Injectable (IV) or (IM): NDC Generic Name: methylprednisolone, hydrocortisone, dexamethasone CPT/HCPCS Procedure Code: J1020, J1030, J1040, J1720, J2920, J2930 Oral: NDC Generic Name: Cortisone, hydrocortisone, prednisone, prednisolone, methylprednisolone, dexamethasone CPT/HCPCS Procedure Code: J7506, J7509, J7510, J8540	
2.4	OR (4) any previous use of strontium, or sodium fluoride within 6 months before trial entry	CRITERIA NOT APPLIED	Strontium not approved in USA for treatment of osteoprosis. Sodium Fluoride is not used to treat the osteoporosis since 2001/2002 when a RCT and sub meta-analysis showed an increased of risk of fractures in the exp
NA	Patients with a serum calcium level of more than 2.75 mmol per liter or less than 2.00 mmol per liter	N/A	
NA	Patients with a calculated creatinine clearance of less than 30.0 ml per minute at either of two baseline visits or urine dipstick results of more than 2+ for protein, without evidence of contamination or bacteriuria.	N/A	
NA	Written informed consent	N/A	
3	Serious disease that may limit life expectancy to less than 6 months (including sever liver and renal diseases)	Measured 180 days prior to the day of drug initiation: CCI >=10 (life expectancy less than the expected duration of the trial)	

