1.5 Secondary endpoint for replication (assay sensitivity) and RCT finding

Non-vertebral fracture

1.6 Trial estimate

Hazard Ratio, HR = 0.59 (95% CI, 0.42 to 0.83) comparing zoledronic-acid group vs. placebo group during a 3-year period (Black et al., 2007).

Note. The follow-up period of the RWE replication is set at 18months. In the trial, the HR comparing zoledronic-acid group vs. placebo group during an 18-month period is estimated to be ~ 0.745 . The HR at 18 months is defined as the ratio between the cumulative incidences of hip fracture events in the zoledronic-acid and placebo groups ($HR = \frac{CI_{ZA}}{CI_{placebo}}$) measured after 18 months of follow-up. The estimates of the cumulative incidences of hip fracture events have been extracted by the Kaplan-Meier curves reported in the trial using a dedicated software (Graph Grabber 2.0.2, Quintessa Ldt).

2. Person responsible for implementation of replication in Action

[name], MPH, implemented the study design in the Aetion Evidence Platform. She is not responsible for the validity of the design and analytic choices. All implementation steps are recorded, and the implementation history is archived in the platform.

3. Data Source(s)

Optum CDM, IBM® MarketScan®

4. Study Design Diagram

The study design diagram visualizes key aspects of the longitudinal study design for expedited review.

Cohort Entry Date (Day 1) [Dispensation of Zoledronic acid (5 mg, IV administered annually)] OR [Raloxifene (oral tablet administered daily)] INCL: Diagnosis of Osteoporosis Days [Enrollment, 0] **INCL**: Use of meds for osteoporosis INCL: Age ≥ 65 Days [0] EXCL: Amputation or absence of lower limb Days [Enrollment, 0] EXCL: Prior use of Bisphosphonate OR parathyroid hormon Days [-730, 0] EXCL: Treatment and Prevention of Glucocorticoid-Induced Osteoporosis Days [-730, 0] EXCL: Treatment of Paget's Disease of Bone Days [-730, 0] Days [-450, 0] EXCL: Life expectancy less than 6 months (CCl ≥ 10)

Days [-450, 0] EXCL: Malignant neoplasms Days [-365, 0] ons that influence bone metabolism (e.g frome, Anorexia, bulimia, RA, SLE, IBD, hyperthyroidism, etc.) Days [-365, 0] EXCL: conditions/circumstances likely to lead to poor treatment adherence (Alcohol/drug abuse)

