5.2 Important steps for cohort formation

New use of zoledronic acid (exposure) is defined as no use of the exposure drug in the 450 days prior to index date. New users of zoledronic acid will be allowed to receive concomitant therapy with raloxifene before and/or during the study period, similar to the trial. We use the long look-back period of 450 days to define new use because zoledronic acid is given as a yearly infusion; thus, a identifying whether a patient has current zoledronic acid exposure requires at least 365 days of look back. We extended this lookback to 450 days (approximately 15 months) to allow for patients who have a short gap between infusions. To keep the amount of lookback available in the 2 treatment groups equal, New use of raloxifene (comparator, proxy to placebo) was also defined as no use of either exposure or comparator drugs in the 450 days prior to index date.

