5.3 Flowchart of the study cohort assembly

For zoledronic acid vs. raloxifene

	Optı	ım CDM	IBM® Ma	rketScan®
	Excluded Patients	Remaining Patients	Excluded Patients	Remaining Patients
All patients		77,673,639		200,203,908

	-77,476,067	197,572	-	489,107
Did not meet cohort entry criteria			199,714,801	
Excluded due to insufficient enrollment	-52,317	145,255	-164,242	324,865
Excluded due to prior use of referent	-81,791	63,464	-185,458	139,407
Excluded due to prior use of exposure	-9,268	54,196	-29,153	110,254
Excluded because patient qualified in >1 exposure category	-1	54,195	-1	110,253
Excluded based on Inclusion #1 - Age, range 65-89 years	-17,914	36,281	-58,739	51,514
Excluded based on Inclusion #2 - Gender, female [Excluded if Male or Unknown]	-6,080	30,201	-6,857	44,657
Excluded based on Inclusion #3 - Osteoporosis	-3,624	26,577	-3,936	40,721
Excluded based on Exclusion #1 - Oral bisphosphonate use	-6,854	19,723	-10,259	30,462
Excluded based on Exclusion #2.1 - PTH or PTH analogue use	-305	19,418	-814	29,648
Excluded based on Exclusion #2.2 - Anabolic–androgenic steroids (AAS) and	-10	19,408	-32	29,616
growth hormones (GH)				
Excluded based on Exclusion #2.3 - Glucocorticoids use	-1,352	18,056	-1,697	27,919
Excluded based on Exclusion #3 - CCI (180 days) >=10	-196	17,860	-154	27,765
Excluded based on Exclusion #4 - Malignant neoplasm, excluding non-melanoma	-2,461	15,399	-4,141	23,624
skin cancer				
Excluded based on Exclusion #5 - Disorders that influence bone metabolism	-1,426	13,973	-2,235	21,389
Excluded based on Exclusion #6 - Glucocorticoid-Induced Osteoporosis	-4	13,969	-5	21,384
Excluded based on Exclusion #7 - Paget's Disease	-43	13,926	-65	21,319
Excluded based on Exclusion #8 - Alcohol abuse or Drug addiction or Non-	-141	13,785	-137	21,182
compliance	1	10.504	2	21 170
Excluded based on Exclusion #9 - Pregnancy	-1	13,784	-3	21,179
Excluded based on Exclusion #10 - Lower extremity amputation	-18	13,766	-37	21,142
Excluded based on Exclusion #11 - Denosumab use	-53	13,713	-35	21,107
Excluded based on Exclusion #12 - Zoledronic Acid use (for raloxifene users)	-223	13,490	-313	20,794
Excluded based on Exclusion criteria #13 - End-stage renal disease	-5	13,485	-12	20,782
Excluded based on Exclusion criteria #14 - End-stage liver disease	-33	13,452	-66	20,716
Excluded based on Exclusion criteria #15 - Blindness or low vision	-32	13,420	-25	20,691
Excluded based on Exclusion criteria #16 - Abaloparatide	-0	13,420	-0	20,691

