	8	Other conditions/circumstances likely to lead to poor treatment adherence	Measured 365 days prior to drug initiation in any diagnosis position in inpatient or outpatient care setting: Alcohol Abuse or Dependence ICD-9 diagnosis: 291.xx, 303.xx, 305.0x, 571.0x, 571.1x, 571.2x, 571.3x, 357.5x, 425.5x, E860.0x (CMS has not released mapping for new ICD10 for this code), V11.3x ICD-10 diagnosis: F10.x, K70.x, G62.1, I42.6, 099.31x OR Drug Abuse or Dependence ICD-9 diagnosis: 292.xx, 304.xx, 305.2x-305.9x, 648.3x ICD-10 diagnosis: F11.x, F12.x, F13.x, F14.x, F15.x, F16.x, F17.2x, F18.x, F19.x, F55.2, G62.0, 099.32x OR Non-compliance: ICD-9 diagnosis: V45.12, V15.81 ICD-10 diagnosis: Z91.19, Z91.15	
	9	Pregnancy (even though it is very unlikely to found cases we add this criteria to make sure all women are postmenopausal)	Measured 180 days prior to and including day of drug initiation in any diagnosis position and inpatient or outpatient care setting Pregnancy (see "Pregnancy codes")	
1		Low fracture risk or unlikely to benefit: Amputee	Measured time of enrollment to prior to the day of drug initiation inpatient (any position), outpatient (any position): ICD-9 Diagnosis: Acquired absence of lower limb: V49.7x, Traumatic amputation 895.x, 896.x, 897.x ICD-9 Procedure: Amputation Of Lower Limb: 84.1xx, 84.25-84.28 ICD-10 Diagnosis: Acquired absence of lower limb: Z89.4xx, Z89.5xx, Z89.6xx, Traumatic amputation: S78.xxx ICD-10 Procedure: Detachment of lower limb: 0Y6xxx	
1	11	Zoledronic acid use (to exclude ZA use in the raloxifene group)	Measured 450 (I year + 90 days) prior to the day of drug initiation: (same as exposure)	
1	12	Denosumab use	Measured 450 (1 year +90 days) prior to the day of drug initiation:	
				1

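### Zoledronic acid is left out of the 730-day bisphosphonate exclusion and screened for 450 days only, so women infused 451 to 730 days before index can enter either arm

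*Protocol*

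**What the plan says.** Two look-back lengths apply to bisphosphonates.

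- **730 days, stated as a class.** The design diagram (Protocol Section 4, Figure 1) has "EXCL: Prior use of Bisphosphonate OR parathyroid hormon Days [-730, 0". Appendix A, Exclusion 1, implements it as "Measured 730 days (2 years) prior to the day of drug initiation: Generic names: Alendronate, Ibandronate, Risedronate, Pamidronate, Etidronate, Tiludronate". Zoledronic acid is not among the six names.
- **450 days, for zoledronic acid.** Section 5.2 says "New use of zoledronic acid (exposure) is defined as no use of the exposure drug in the 450 days prior to index date", and Appendix A repeats it as "Exposure: new-use of Zoledronic acid (washout 450 days". For raloxifene, Section 5.2 defines new use as "no use of either exposure or comparator drugs in the 450 days prior to index date". Appendix A, Exclusion 11, screens raloxifene users with "Measured 450 (I year + 90 days) prior to the day of drug initiation: (same as exposure". The flowchart numbers this criterion 12: "Excluded based on Exclusion #12 - Zoledronic Acid use (for raloxifene users".

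Section 5.2 explains the 450 days by the yearly infusion schedule plus a margin for a short gap between infusions, and by the wish for equal look-back in the two groups. Section 5.1 requires 450 days of continuous enrollment.

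**The concern.** Read literally, the rules treat the study drug more leniently than the other bisphosphonates. A single alendronate fill 700 days before index excludes a woman, but a zoledronic acid infusion 460 days before index does not.

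Both arms are affected.

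- **Raloxifene arm.** It is there to represent placebo. The primary analysis follows zoledronic acid initiators for 540 days after infusion (Section 6.3.2). A woman infused 451 to 539 days before starting raloxifene is still inside that horizon when she enters the comparator. Any residual benefit lowers the comparator's fracture rate and pulls the HR towards 1.
- **Zoledronic acid arm.** A woman re-infused after a gap of 451 to 730 days is labelled a new initiator although she is a returning user.

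Appendix B, Table 1, has no row for prior zoledronic acid. It has a row for prior bisphosphonate use, but does not state that row's drugs or window.

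**Working it through.** **1. The windows side by side**

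| Screen | Window (days before index) | Covers zoledronic acid? |
|---|---|---|
| Design diagram, bisphosphonates | 730 to 0 | As a class, yes |
| Appendix A, Exclusion 1 | 730 | No, six other drugs |
| New use of zoledronic acid (Sections 5.2, 6.1; Appendix A) | 450 | Yes |
| New use of raloxifene (Sections 5.2, 6.1) | 450 | Yes |
| Appendix A, Exclusion 11 (raloxifene users) | 450 | Yes |

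No criterion looks for zoledronic acid on days -730 to -451, a span of 730 - 451 + 1 = 280 days.

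**2. The plan's power figure**

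Section 10 gives, for the pooled match, 18,028 women, a risk of 10.40 per 1,000, HR 0.59 and two-sided alpha 0.05.

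- Events D = 18,028 x 10.40/1,000 = 187.49, as stated.
- Power = Φ(|ln HR| x √(D/4) - 1.96) = Φ(0.5276 x 6.846 - 1.96) = 0.951, against 0.950774 stated. It reproduces.
- SE(ln HR) is about 2/√187.49 = 0.146.

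**3. Illustration for the comparator arm**

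Suppose a share f of raloxifene users carries a residual hazard ratio r from an earlier infusion. Neither value is in the document; both are assumptions.

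- Observed HR = HR/(1 - f(1 - r)).
- Events = D x (HR + 1 - f(1 - r))/(HR + 1).

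With HR = 0.59 and r = 0.59, so that the full effect persists:

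| f | Observed HR | Shift in ln HR, as share of one SE | Events | Pooled power |
|---|---|---|---|---|
| 0 | 0.590 | none | 187.5 | 0.951 |
| 1% | 0.592 | 0.004, 3% | 187.0 | 0.947 |
| 3% | 0.597 | 0.012, 8% | 186.0 | 0.940 |
| 5% | 0.602 | 0.021, 14% | 185.1 | 0.932 |
| 10% | 0.615 | 0.042, 29% | 182.7 | 0.907 |

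With a weaker residual effect (r = 0.745), power at f = 5% is 0.940.

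Section 1.6 puts the trial's 18-month HR at about 0.745. With that as the true HR and the same number of events, power is 0.522 without contamination. At f = 5% it is 0.461 with r = 0.59 and 0.484 with r = 0.745.

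**4. The flowchart counts**

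The flowchart (Section 5.3) first removes prior users of the exposure drug: 9,268 + 29,153 = 38,421 patients. A later step removes a further 223 + 313 = 536 for zoledronic acid use among raloxifene users. Both screens are written as 450 days, so the second should find almost nobody. The document does not explain why it finds 536.

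**The case against.** The strongest defence is that 450 days is a disclosed and reasoned choice. It matches the enrollment requirement and gives both arms the same guaranteed look-back. Denosumab and romosozumab also get 450 days. The 730-day list follows the bisphosphonates named in the trial's own criterion, and the flowchart labels that step as oral bisphosphonates. The protocol also tolerates older bisphosphonate use: Inclusion 2 accepts use more than 730 days back, and Table 1 counts prior bisphosphonate use in 4,022 of 13,509 unmatched raloxifene users (29.8%).

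Part of this stands. The choice is disclosed, and the likely effect is small beside the sampling error. The rest does not settle the point. The Section 5.2 rationale concerns current exposure and gives no reason for a shorter look-back for prior zoledronic acid than for the six other bisphosphonates. The trial criterion names its drugs as examples, and the implementation already extends them by adding ibandronate. The design diagram promises the class.

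A reader might infer more than the documents support, in three ways:

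- **That about 330 contaminated women remain in the comparator**, from 536 x 280/450. The 536 were removed after a nominally identical screen, so it is unknown what they represent: a different window, the handling of day 0 or different code matching. If the later step ran a longer window, part of the gap is already closed. The figure cannot anchor an extrapolation.
- **That the 38,421 show how common repeat infusion is among eligible women.** They are patients counted before the age, sex, osteoporosis and malignancy filters. The sex filter alone later removes 6,080 and 6,857.
- **That the primary result is materially biased in a known direction.** Comparator contamination pulls the HR towards 1, but the effect of returning users in the exposed arm is not established.

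**Conclusion.** The inconsistency is real on the face of the Protocol. The diagram excludes prior bisphosphonate use over 730 days, the drug list omits the study bisphosphonate, and nothing else covers days -730 to -451 in either arm.

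Its size cannot be determined, because the number of women infused in that window is not reported. Under the assumption least favourable to the plan in the table, a fully persistent effect, 5% contamination of the comparator moves the HR from 0.59 to 0.602 and costs about two points of pooled power. The cost is larger at an HR of 0.745, where power is already low. These figures depend on assumed f and r and ignore the exposed arm. The net direction is unknown.

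The correction is worth making because it is cheap and Section 13 shows no date for the comparative analyses. It is not evidence that the design fails.

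**What to change.** Keep the 450-day enrollment requirement and the 450-day new-use definition. Add zoledronic acid to the Exclusion 1 screen for both arms over days -730 to -1, using available history as for the six listed drugs. Day 0 must be left out for zoledronic acid, or the index infusion would remove the whole exposed arm.

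Before re-running, confirm which windows and codes were used in the two flowchart steps that screen for zoledronic acid, and explain the 536 removals. Align the criterion numbers at the same time: zoledronic acid and denosumab are 11 and 12 in Appendix A but 12 and 11 in the flowchart. Then re-run the match and report the removals by arm and database.

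The cost is one drug added to a screen that already runs, one re-match, and a probably small loss of matched women. Days -730 to -451 will be incompletely observed for women with only 450 days of enrollment. That limit already applies to the six listed drugs, so it is no reason to treat zoledronic acid differently, but it should be stated.
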